### **Summary of Analytic Plan:**

We will use graphical and numerical summaries to describe the outcomes at each assessment point. If distributional assumptions for particular statistical procedures are violated, appropriate transformations will be made or non-parametric tests will be used. All primary and secondary analyses will follow the intent-to-treat principle; all participants will be analyzed in the group to which their clinic was assigned irrespective of their post-randomization behavior, and all participants will be analyzed using multiple imputation techniques. Hypothesis-driven comparisons will be made with control of the type I error rate at 0.05 (two-sided).

**Preliminary Analysis.** We will examine data for out of range values. Descriptive statistics will be generated regarding practice characteristics such as size (small, medium, large), practice type (hospital-based practice, Federally Qualified Health Center, neighborhood health center), and patient mix (pediatrics, adult/pediatrics) to help to understand the sample as well as the generalizability of study findings. We will determine whether there are differences at baseline between the eMPI and eUC providers and patients in demographics and background characteristics. This will include analogs of t-tests (or Wilcoxon rank sum tests) for continuous variables and chi-square (or Fisher's Exact) tests for categorical variables adjusted by generalized estimating equation (GEE) methods for the clustering induced by providers within clinics.

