### **Patient-Level Variables**

**Clinical/Functional Outcomes** will be collected from caregivers of 512 children (Table 5).

**1. Asthma Symptoms:** We will assess number of symptom-free days (SFDs) (**secondary outcome measure**) at baseline, 3 months to determine short-term effectiveness of the intervention, and at 6, 9, and 12 month follow-up evaluations to assess long-term intervention effects. This outcome

measure is consistent with the symptom monitoring recommended by the national guidelines and has been suggested as a useful endpoint for pediatric asthma studies. Caregivers will be asked to report the number of days their child experiences *no* symptoms of asthma (defined as 24 hours with no coughing, wheezing, chest tightness, or shortness of breath) in the past 2 weeks. We will also assess asthma control with the Asthma Control Test.

**2. Healthcare Utilization:** Caregivers will report child's healthcare utilization at baseline and each follow-up. In addition, EHR data will be reviewed at each follow-up to assess for office visits (acute and routine), emergency department visits and hospitalizations. We will also evaluate healthcare utilization outcomes from the EHR data review for all patients with persistent or uncontrolled asthma (~5,000) across practices.

**3. Quality of Life:** Quality of life will be measured at baseline and each follow-up using Juniper's Pediatric Asthma Caregiver's Quality of Life Questionnaire (PACQLQ). The PACQLQ is a standard instrument used to assess the quality of life of caretakers of children with asthma, and provides a quantitative score that reflects answers to questions about the burden of caring for a child with asthma.

**4. Functional Severity:** Functional limitations of the child will be assessed at baseline and each follow-up evaluation using a subscale from the Children's Health Survey for Asthma. The child activity subscale includes 5 items on limitations to the child's activities due to asthma (Cronbach's alpha .87-.89).

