**Aim 2. To determine whether consistent use of eMPI leads to both short- and long-term improvements in clinical outcomes.** In this Aim, we will compare the change from baseline to each of the follow up (FU) time points (i.e., 3, 6, 9, and 12 months) in number of SFDs between eMPI and eUC patients using intent-to-treat principles. We will employ the generalized linear model (GLM) with identity link function for this comparison. The analysis model is of the form  $EY_{ij} = \alpha + \beta I_i + \sum \gamma_j T_{ij} + \sum \delta_j I_j T_{ij}$ , where for subject  $i$   $Y_{ij}$  is the number of SFDs for at time  $j$ ,  $I_i$  denotes group indicator for eMPI group (vs. eUC), and  $T_{ij}$  is the indicator for time at FU $j$  evaluation (vs. baseline). The regression coefficient  $\delta_j$  corresponding to the group-by-time interaction term estimates the difference in average change of SFDs at FU $j$  evaluation vs. baseline, comparing eMPI to eUC groups, and thus represents the effect of intervention on the SFDs. We will use generalized estimating equations (GEE) methodology to account for within-subject correlation due to multiple assessments for the same subject as well as the within-provider and within-practice correlations due to cluster sampling. We will also determine whether or not the corrective actions taken mediates the effect of intervention on outcomes; we will use the test of joint significance of the 2 paths involving a potential mediator, which best balance Type I error and statistical power. A variable  $M$  will be declared a mediator only if both the test of the regression coefficient of the explanatory factor  $X$  on the mediator and the test of the coefficient of the mediator on the outcome variable  $Y$  controlling for  $X$  are significant at level alpha = 0.05, 2-tailed. This approach allows for partial mediation which we fully expect to occur. In subsequent analyses we will estimate the indirect path effect with 95% confidence intervals using the asymmetric distribution of products method. Further exploration of causal mediation will

follow the methods of Imai et al. We will also examine whether the effect of intervention on SFDs is mediated by provider competencies, provider/caregiver communication or caregiver self-efficacy.

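### A general fallback rule allows the pre-specified symptom-free-day analysis to be replaced after the data are seen, and nothing says that the Aim 2 model takes precedence

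*Combined protocol and SAP*

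**What the plan says.** The opening paragraph of the Summary of Analytic Plan contains the rule "If distributional assumptions for particular statistical procedures are violated, appropriate transformations will be made or non-parametric tests will be used". It stands between a sentence on describing the outcomes at each assessment and one on intention-to-treat for all primary and secondary analyses. The same paragraph sets a two-sided type I error rate of 0.05 for hypothesis-driven comparisons.

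Aim 2 names the SFD analysis: "We will employ the generalized linear model (GLM) with identity link function for this comparison". Its group-by-time coefficient delta_j "estimates the difference in average change of SFDs at FU" j relative to baseline, so the effect is in days. GEE is used to "account for within-subject correlation due to multiple assessments for the same subject as well as the within-provider and within-practice correlations due to cluster sampling". Aim 2 names no distributional check and no alternative method. It does not state the type of standard error or any correction for a small number of practices.

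Patient-Level Variables (Asthma Symptoms) defines SFDs by caregiver recall over two weeks. A range of 0 to 14 whole days follows, although no range, distribution or ceiling share is given. Cluster-adjusted versions of rank tests appear only under Preliminary Analysis, for baseline comparisons, as tests "adjusted by generalized estimating equation (GEE) methods for the clustering induced by providers within clinics".

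**The concern.** Two statements govern the same outcome and neither is ranked above the other. One fixes a model in days. The other allows a different scale or a different class of test if an unspecified assumption is judged to fail. A bounded count with a probable ceiling invites that judgement.

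Three things are at stake for the main clinical outcome:

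- **The effect measure.** A transformed outcome no longer gives a difference in days, and an ordinary rank test gives no delta_j.
- **Later steps.** The mediation tests in Aim 2 and the pooling of multiple imputations need coefficients and variances. A bare rank-test p-value supplies neither.
- **The error rate.** No cluster adjustment is stated for a substitute outcome test.

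**Working it through.** **1. Inputs.** From the Aim 2 Power Analysis: 460 children analysed, 230 per group, ICC 0.03 (the same value for provider and practice), 80% power. From Subjects and Setting: 22 practices planned, 18 participating. From the Background: about 200 providers. From the Summary of Analytic Plan: alpha 0.05, two-sided. SFD means, SDs and ceiling shares are not given, so those used below are assumptions.

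**2. The plan's own figure.** The only figure for Hypothesis 2a is a detectable standardized effect of 0.29. The formula is d = (1.960 + 0.842) × √(2 × DE / 230), with DE = 1 + (m − 1) × 0.03 and m children per cluster. It gives 0.261 without clustering, 0.266 with 200 providers, 0.330 with 22 practices and 0.344 with 18. A value of 0.29 needs DE = (0.29 / 0.2612)² = 1.23, so m is about 8.7. The stated cluster counts do not reproduce 0.29, and no cluster size is given. That is a separate question, and nothing below depends on it.

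**3. Is a normality check likely to fail?** Null data were simulated for 460 children in equal-sized practices. SFDs were rounded and clipped to 0–14, with within-child correlation 0.4 and 3,000 runs per row. The three scenarios had underlying means (SD) of 9 to 11 (4.0), 9 to 12 (4.5) and 10 to 13 (5.0), giving 27%, 37% and 46% at the ceiling at follow-up. Shapiro–Wilk rejected normality of follow-up SFDs in every run. It rejected normality of the change scores, which Hypothesis 2a compares, in 59% to 99.5% of runs. Failure is therefore very likely, but not certain on the change scale.

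**4. Does the planned mean comparison need normality?** Type I error for change in SFDs, nominal 0.05:

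| Practices | Ceiling | ICC of change | Rank-sum, no cluster adjustment | Robust mean difference, z | Robust mean difference, t with K−2 df |
|---|---|---|---|---|---|
| 22 | 27% | 0.036 | 0.127 | 0.078 | 0.046 |
| 22 | 37% | 0.030 | 0.115 | 0.074 | 0.053 |
| 22 | 46% | 0.027 | 0.111 | 0.077 | 0.049 |
| 18 | 27% | 0.036 | 0.156 | 0.087 | 0.053 |
| 18 | 37% | 0.031 | 0.139 | 0.088 | 0.053 |
| 18 | 46% | 0.026 | 0.119 | 0.079 | 0.046 |

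The Monte Carlo standard error near 0.05 is √(0.05 × 0.95 / 3000) = 0.004. The comparison in days holds its level with a small-sample reference (t with K−2 df, standard error multiplied by √(K/(K−2))), despite the ceiling. With an uncorrected z reference it does not. That inflation comes from the small number of practices: the same skewed data hold their level under the t reference.

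**5. Cost of losing the cluster adjustment, by formula.** Type I error = 2 × [1 − Φ(1.96 / √DE)].

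- 22 practices: m = 460/22 = 20.9, DE = 1.597, result 0.121.
- 18 practices: m = 460/18 = 25.6, DE = 1.737, result 0.137.

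The simulated rank-sum column (0.11 to 0.16) agrees. An unadjusted t-test on days gave 0.115 to 0.160, so the harm comes from ignoring practices, not from using ranks.

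**6. Cost of losing the days scale.** Take an invented example in which eMPI goes from 8 to 11 days and eUC from 7 to 10, a gain of 3 days in each. On log(15 − SFD), the difference in change is ln(4/7) − ln(5/8) = −0.560 + 0.470 = −0.09, an apparent benefit of eMPI. The documents name no transformation; the example shows only that the contrast changes with the scale.

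**The case against.** The strongest reply is that Aim 2 already fixes the analysis, and that the general rule applies only when an assumption of the procedure in use is violated. An identity-link GEE with robust variance does not assume normal outcomes, so non-normal SFDs violate nothing and the rule never fires. This is sound statistics, and the rule does not compel a departure. However, Aim 2 names neither robust standard errors nor the assumptions to be checked, and it does not say that it prevails. The reply therefore shows how the plan could be read, not what it says.

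Three stronger readings are tempting, and the documents do not support them:

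- **That the Hypothesis 2a analysis is left to be chosen after the data are seen.** It is named in advance; the gap is that it can be replaced.
- **That the trial will use an unadjusted rank test.** No section proposes one for SFDs. Aim 2 requires cluster adjustment, and the only Wilcoxon test named in the plan is to be GEE-adjusted. The figures of 0.12 to 0.14 are a worst case.
- **That any switch inflates type I error.** With 18 practices of 26 children, ICC 0.03, two assumed ceilinged distributions and 4,000 null runs each, failing Shapiro–Wilk led to one cluster-level rank or log test. Type I error was 4.8 to 5.2%. Taking whichever of three cluster-adjusted tests is significant gave 6.1 to 6.9% across two sets of simulations, but the rule is triggered by distribution, not by significance.

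**Conclusion.** The point holds as an ambiguity that should be closed. The general rule has no named trigger, replacement or scope, and SFDs are not exempt, so the pre-specified days-scale analysis can be replaced after the data are seen. Replacement gains no validity, because the planned mean comparison had a type I error of 0.046 to 0.053 on ceilinged 0–14 data with a small-sample reference. The certain cost of a transformation or ordinary rank test is the effect in days. The possible cost is the cluster adjustment, with worst-case type I error of 0.121 (22 practices) or 0.137 (18 practices) at ICC 0.03.

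The request for a small-sample correction stands on its own: with 18 or 22 practices, an uncorrected z reference rejected 7.4 to 8.8% of the time under the null. These simulated figures rest on assumed SFD distributions, equal practice sizes and an ICC of change near 0.03. SFDs are a secondary outcome, though the main clinical one. The Aim 1 permutation test is already non-parametric and is not affected.

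**What to change.** In Aim 2, state that the identity-link GEE in days is the Hypothesis 2a analysis whatever the observed distribution of SFDs. Add that standard errors are cluster-robust at practice level with a small-sample correction, for example a t reference with K − 2 = 16 df for 18 practices.

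In the Summary of Analytic Plan, limit the fallback sentence to descriptive and preliminary comparisons and to named, cluster-adjusted sensitivity analyses. If a check that respects the bounds is wanted, name one, such as a binomial GEE for days out of 14 with practice clustering. Aim 1 needs no change.

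The cost is SAP wording, and the sample size stays the same. The team gives up the freedom to move to a rank test that might be more powerful for a particular shape. A t reference with 16 df also raises the detectable effect by about 6 to 7% over the normal approximation: (2.120 + 0.865) / (1.960 + 0.842) = 1.065. That is the price of holding the error rate near the stated 0.05.

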### **Aim 1. To test the impact of eMPI on provider adoption of asthma management guidelines.**

The **primary outcome** is a clinic-level variable measured by the ratio of number of visits with  $\geq 1$  guideline-based corrective actions to the number of visits by patients aged 2-12 years with persistent or uncontrolled asthma at the time of visit. The **primary null hypothesis** is that there is no difference between eMPI and eUC clinics in the mean proportion of visits where the necessary corrective actions were taken. To test this null hypothesis, we will use a matched-pairs randomization (or permutation test) at the 0.05 two-tailed level of

significance. The permutation test will account for the fact that clinics (rather than providers) are randomized and that the randomization will be performed within clinic pairs. Each pair of clinics will produce a matched difference in the proportions of corrective actions, and under  $H_0$  the randomization can be viewed as attaching a random plus or minus sign. Thus there will be  $2^{11} = 2,048$  possible signed permutations, allowing a two-tailed p-value as significant as  $2/2,048 < 0.001$  (if all 11 pairs show a greater proportion of corrective actions taken by the eMPI practices). Assuming no important practice characteristics are significantly out of balance (at two-tailed  $p < 0.01$ ), the permutation test will comprise the primary analysis. If any important clinic characteristics are significantly imbalanced at  $p < 0.01$ , we will adjust for such variables in a linear regression model and report the adjusted intervention coefficient as the primary result. We will also examine for a clinic-size (or provider-type) by intervention interaction. If not significant at the 5% level, the above approach will be used to provide the primary results. If significant, we will attempt to identify factors that affect the primary outcomes and might differ between clinics (or provider types). If including such factors removes the interaction, we will quote the adjusted intervention effect from the model including such factors. If not, we will quote two intervention effects (for large and small clinics) leaving the interaction unresolved.

**Power Analysis.** We conservatively estimate that the mean difference between eMPI and eUC clinics in the proportion of visits where the necessary corrective actions were taken will be at least 25 percentage points. To express this as a standardized effect size, we assume the standard deviation of the paired differences in the proportion of corrective actions will be no more than 0.2, based on several mock data sets generated by the investigators reflecting their clinical experience and best estimates. We present one generated data set in Table 6 for illustration. This hypothetical data set has an average matched difference in proportions of 0.246 (about 25 percentage points) with standard deviation 0.142 (14.2 percentage points). Our assumption of a standard deviation of 0.2 or 20 percentage points is thus about 50% larger than in this illustrative example.

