## B. Subjects and Setting

Outpatient practices (n=22) that are part of Montefiore Health System will participate in the study (see Letter of Support). These 22 practices are located throughout the Bronx, NY, represent different practice types, and have participated in several of our prior studies (Table 3). Though there were initially 22 proposed outpatient practices, two practices were closed, two practices (FCC-B and FCC-C) were combined as a single site given that they serve patients in the same facility, and one practice was excluded given no pairing available, resulting in a total n=18 participating outpatient practices. The number of children with asthma across practices (N=10,109) of whom we estimate ~ 50% (N=5,000) to have persistent or uncontrolled asthma is sufficient to meet our sample size needs. A subset of 512 children will be recruited over 4 years (~128 participants each year) to obtain clinical outcomes data that are not in the EHR.

Table 1. Primary Care Practices*					
Site	Practice Type	Provider Type	# 2-12yr olds in practice	# 2-12yr olds with asthma	# visits for 2-12yr olds with asthma
Astor Avenue	NHC	Pediatrics	3,075	576	1,012
Bronx East	NHC	Pediatrics	4,775	884	1,516
Burke Avenue	NHC	Pediatrics/Family MD	1,102	117	196
Castle Hill	FQHC	Family MD	814	97	135
CFCC	FQHC	Pediatrics	5,791	1,144	1,824
CHCC	FQHC	Pediatrics	4,658	1,332	2,488
Co-op Bartow Ave	NHC	Pediatrics	2,485	634	1,059
Eastchester	NHC	Pediatrics	1,350	325	703
FCC - B	Hospital Clinic	Pediatrics	3,671	684	1,028
FCC - C	Hospital Clinic	Pediatrics	3,470	805	1,300
FHC	FQHC	Family MD	1,739	339	606
Grand Concourse	NHC	Pediatrics/Family MD	3,133	540	868
Grand UCC	NHC	Pediatrics/Family MD	2,950	235	262
HIP Cross County	NHC	Pediatrics/Family MD	3,058	272	385
MAP-8	Hospital Clinic	Pediatrics	2,935	631	1,551
Marble Hill	NHC	Pediatrics/Family MD	1,143	186	294
University Avenue	FQHC	Pediatrics/Family MD	1,697	344	645
Verde Clinic	NHC	Family MD	359	78	146
Wakefield	NHC	Pediatrics	354	309	600
West Farms	FQHC	Family MD	954	215	368
White Plains Road	NHC	Pediatrics/Family MD	1,204	174	273
Williamsbridge	FQHC	Family MD	1,059	188	308
TOTAL	-	-	51,776	10,109	17,567

FQHC=Federally Qualified Health Center; NHC=Neighborhood Health Center. \*Number of patients seen between 1/1/14-12/31/14

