**Randomization:** Prior to participant enrollment, each practice will be matched into 11 pairs based on size of the practice and provider type (Table 1). Practices will then be randomly selected within each pair as an eMPI or a eUC site. Practices will join in 4 waves over the course of 4 years (4-6 practices/year). Each practice will remain in the study for 24 months and receive \$500 donation to thank them for participation.

**Inclusion Criteria:** The criteria listed below will apply to ~5,000 children from eMPI and eUC practices. We will obtain a waiver of consent to be able to review EHR data by practice.

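### Aim 1 lets a 5% interaction test on the outcome data displace the planned primary analysis, and one of the two endings that follow cannot decide the single primary null hypothesis

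*Combined protocol and SAP*

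**What the plan says.** Aim 1 gives a single null hypothesis, that the arms do not differ in the mean proportion of visits with corrective action, and a single test: "To test this null hypothesis, we will use a matched-pairs randomization (or permutation test) at the 0.05 two-tailed level". Two conditions then bear on which analysis is primary.

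- **Imbalance.** If an important clinic characteristic differs between arms at p<0.01, a regression coefficient adjusted for it becomes the primary result.
- **Interaction.** A clinic-size (or provider-type) by intervention interaction is examined. "If not significant at the 5% level, the above approach will be used to provide the primary results". The approach referred to is the permutation test together with its imbalance exception.

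If the interaction is significant, the team looks for factors related to the outcome that might differ between clinics or provider types. There are two endings. First: "If including such factors removes the interaction, we will quote the adjusted intervention effect from the model including such factors". Second, if the interaction remains: "we will quote two intervention effects (for large and small clinics) leaving the interaction unresolved".

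The Summary of Analytic Plan commits to two-sided type I error control at 0.05 for hypothesis-driven comparisons. It does not say how that applies after a significant interaction. Under Randomization, "each practice will be matched into 11 pairs based on size of the practice and provider type". Section B later reports closures, a merger and an exclusion, "resulting in a total n=18 participating outpatient practices".

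**The concern.** Which analysis is primary depends on a test of the same outcome data. When the interaction is significant, the planned analysis loses its primary role, even if it rejects the null clearly.

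The two endings are not equally weak. The adjusted ending gives one coefficient, which could be tested at 0.05, but the plan does not say that it will be. Its adjustment factors are found by a search made after the outcomes are known, with no candidate list for that step. The two-effects ending gives two numbers and no rule that turns them into a decision on one null hypothesis.

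The gate itself is also not fully defined. No interaction model is given. Clinic-Level Variables has three practice sizes, while the two-effects ending names only large and small. A provider-type interaction has no two-effects form at all. At stake is whether a trial that meets its planned criterion has a stated primary conclusion.

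**Working it through.** **1. The plan's own figures.** The Aim 1 power analysis uses a difference of 0.25, SD of paired differences 0.20, 11 pairs and 10 df. The non-centrality is 1.25 × √11 = 4.15, and the non-central t power is 96.1%, which agrees with the stated power above 95%. The smallest two-tailed permutation p-value is 2/2,048 = 0.00098, which also agrees. Table 6 sums to 2.70, so the mean is 2.70/11 = 0.245 (printed as 0.246) with SD 0.142.

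**2. Current number of pairs.** 18 practices / 2 = 9 pairs. This is an inference, since the Aim 1 text still uses 11. With 9 pairs the paired-t power at the same inputs is 90.6%, and there are 2^9 = 512 sign permutations.

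**3. Can the planned method decide within size groups?** The smallest two-tailed p-value for k pairs is 2/2^k. A 4/5 split of 9 pairs gives 0.125 and 0.0625, so neither group could reach 0.05. A 5/6 split of 11 pairs gives 0.0625 and 0.031. The permutation test therefore cannot be carried over to the two-effects ending with 9 pairs split this way.

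**4. How often is a significant result displaced?** The plan gives no interaction model, so two were tried, each at 5%:

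- (a) Pooled two-sample t on pair differences: t = (mean of group 1 − mean of group 2) / [s√(1/4 + 1/5)], 7 df.
- (b) Regression on the 18 clinics with arm, size and arm × size and no pair term: the same numerator over s√[2(1/4 + 1/5)], 18 − 4 = 14 df. The within-pair correlation is ρ, and the clinic SD is 0.2/√[2(1 − ρ)], so that pair differences keep SD 0.2.

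Assumed, not in the documents: normal outcomes, one two-level modifier, a 4/5 split, and ρ of 0.3 or 0.5. There were 100,000 runs per row. The sign-flip test was enumerated in full.

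| True effect in the two groups (points) | Gate | Permutation p≤0.05 | Gate fires | Both: displaced |
|---|---|---|---|---|
| 25 / 25 | (a) | 89.4% | 5.1% | 4.6% |
| 25 / 25 | (b) ρ=0.3 | 89.3% | 2.3% | 1.9% |
| 25 / 25 | (b) ρ=0.5 | 89.4% | 1.1% | 0.8% |
| 30 / 20 | (a) | 86.5% | 9.8% | 8.2% |
| 30 / 20 | (b) ρ=0.3 | 86.4% | 5.7% | 4.2% |
| 30 / 20 | (b) ρ=0.5 | 86.5% | 2.9% | 2.0% |
| 35 / 15 | (a) | 79.4% | 25.2% | 18.6% |
| 35 / 15 | (b) ρ=0.3 | 79.5% | 18.2% | 12.0% |
| 35 / 15 | (b) ρ=0.5 | 79.2% | 10.6% | 6.5% |

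The first block uses the plan's own effect and SD. The other two assume a true interaction. Gate (b) fires less often because it ignores the pairing and so overstates the standard error when ρ>0.

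**5. Limits of these rates.** They count every trial in which the gate fires and the permutation test is significant. The factor search is not modelled, so trials that would end in one adjusted effect are included. The table also covers one modifier. If size and provider type were both tested, independently, at 5%, the chance of at least one false signal would be 1 − 0.95² = 9.75%.

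**6. Under the null.** Across the gates tried, the permutation test alone rejects in 4.6-4.7% of trials. If gate-firing trials are not counted as rejections, the rate is 4.4-4.7%.

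**The case against.** The best defence is that the rule was written in advance and answers a sensible question: if large and small clinics really respond differently, two effects describe the result better than one average. That stands as a reason to report the two effects. It is not a reason to leave the primary null undecided, and both can be done. On this view the displaced share in the 35/15 rows is not all harm.

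A second defence is that the adjusted ending gives a single coefficient, to which the general 0.05 level could apply. That also stands. It confines the missing verdict to the two-effects ending and leaves the adjusted ending open only to the criticism of its outcome-driven search.

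A third is that little of substance is lost. With gate (a) and a uniform 25-point effect, both group effects are positive in over 99% of displaced trials. This too is fair: the gap lies in the formal conclusion more than in what a reader would see.

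A reader might go further and infer that the rule inflates type I error. The documents do not support that. Inflation would require counting significance in either size group as success, and the plan states no such rule. It says only that effects will be quoted, and read descriptively they leave the error rate below 0.05.

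One might also argue that the permutation test decides regardless and the rest is reporting. The wording quoted above makes it the source of the primary result only when the interaction is not significant.

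**Conclusion.** The point holds in this form. An interaction tested at 5% on the outcome data can displace the planned primary analysis. One ending then gives no decision on the single null, and the other adjusts for factors chosen after the data are seen. This follows from the text alone.

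The size depends on assumptions. On the plan's effect and SD, with no true interaction and 9 inferred pairs, a significant permutation result is displaced in roughly 1-5% of trials. With an assumed 35 versus 15 points it is about 6-19%. The range reflects the unstated interaction model and within-pair correlation. For a given gate these are upper bounds on trials left without a verdict. It would be wrong to read them as the share of trials with no conclusion, or to say that every significant interaction leaves none. No type I error inflation has been shown. The matter should be fixed before analysis.

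**What to change.** State in Aim 1 that the interaction test does not change which analysis decides the primary hypothesis, and that the within-pair sign-permutation test on all pairs decides it.

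Say in the same place how this fits with the p<0.01 imbalance rule, so that the section does not hold two competing primary rules. Either report the imbalance-adjusted regression beside the permutation test as a sensitivity analysis, or keep that rule as the one stated exception.

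Report the size and provider-type interactions, the stratum effects with confidence intervals and any factor-adjusted model as secondary results. Fix in advance the interaction model, how the three practice sizes become the groups to be compared, and the provider-type grouping.

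The cost is SAP wording only. No new data and no change in sample size are needed, and every planned exploration is kept.
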